#### Sensitivity analyses

*Key sensitivity analysis*: To augment causal inference from the primary analysis and evaluate for the possibility of non-parallel trends in the primary outcome at intervention versus control hospitals during the preintervention phase, we will perform a sensitivity analysis evaluating the adjusted primary outcome (door-toantibiotic time) with a multi-group interrupted time series analysis. The following segmented regression suggested by Ryan et.al. will be used to estimate the effect of the Code Sepsis intervention on door-toantibiotic time:

$$Y_{igt} = \beta_0 + \beta_1 Time + \beta_2 (Time * Int_g) + \beta_3 Post_t + \beta_4 (Int_g * Post_t) + \beta_5 Cov$$

Where  $Y_{igt}$  is the door-to-antibiotic time for patient *i* treated at an intervention or non-intervention ED *g* at pre- or post-intervention time *t*. *Time* is a continuous variable indicating the bi-weekly count from the start of the observation period; *Int* is a binary indicator for the subject being treated at an intervention hospital; *Post* is a binary indicator for the post intervention period. The  $\beta_4$  parameter from the regression model is interpreted in nearly the same manner as the primary outcome, in that it estimates the adjusted differential change in door-to-antibiotic time between the control and CodeSepsis hospitals. This model allows for the trends to differ between the intervention and control hospitals during the pre-intervention phase. We will consider the Code Sepsis intervention of have had an impact if  $\beta_4$  is statistically significant and different from zero.

In order to account for the right skew known to exist in door-to-antibiotic time we will use generalized linear gamma regression to estimate the DID. Data from the wash-in phase will be excluded from the sensitivity analysis.

- Other primary outcome sensitivity analyses:
  - Repeat primary analysis among patients in "sepsis high-risk" cohort who received antibiotics in the ED.
  - Repeat primary analysis in the dataset comprising all *encounters* (≥1 encounter per patient) meeting sepsis criteria between ED arrival and ED departure, using generalized linear models with a random effect for patient to account for non-independence.
  - $\circ$   $\,$  Missing data sensitivity analyses as described in the "Missing Data" section  $\,$

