### Data analysis

Analyses for causal inference regarding primary, secondary and safety outcomes will employ a quasi-experimental method called *difference-in-difference* (DID) analysis to control for secular trends and confounding of unknown individual factors associated with the outcome of interest. The DID approach will provide an estimate of the effect of the Code Sepsis intervention on primary, secondary, and safety outcomes by comparing the intervention and control hospitals during the pre- and post-implementation periods (Figure 1).

For the primary outcome, DID analysis will use multivariable linear regression to compare the adjusted mean door-to-

antibiotic time (primary outcome) at the intervention hospital

pre- versus post-implementation of the Code Sepsis protocol using the measured change at contemporaneous control non-intervention hospitals to control for pre-/post-intervention changes not attributable to protocol implementation after adjustment for potential confounders.

The following equation will be used to estimate the adjusted mean differential change in the primary outcome, door to antibiotic time:

$$Y_{igt} = \beta_0 + \beta_1 Int_g + \beta_2 Post_t + \beta_3 (Int_g * Post_t) + \beta_4 Cov$$

Where  $Y_{igt}$  is the door-to-antibiotic time for patient *i* treated at an intervention or non-intervention ED *g* at pre- or post-intervention time *t*. *Int* is a binary indicator for the subject being treated at an intervention hospital; *Post* is a binary indicator the post-intervention period; and *Cov* represents a vector of patient-level covariates. The  $\beta_3$  parameter from the regression model presented above estimates the adjusted mean differential change in door-to-antibiotic time observed in the Code Sepsis intervention hospital compared to the control hospital. We will consider the Code Sepsis intervention to have had an impact if  $\beta_3$  is statistically significant and different from zero.

The parallel trend assumption will be tested using the approach outlined by Callaway and Sant'Anna. This approach allows for testing the parallel trend assumption after conditioning on covariates. This approach is

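### The interrupted time series model named as the key sensitivity analysis has no hospital main effect, so a baseline level gap between hospitals appears as a Code Sepsis effect of about the same size and opposite sign

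*SAP*

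**What the plan says.** In the SAP, under Sensitivity analyses, the key sensitivity analysis is a segmented regression: "Y_{igt} = \beta_0 + \beta_1 Time + \beta_2 (Time * Int_g) + \beta_3 Post_t + \beta_4 (Int_g * Post_t) + \beta_5 Cov". Time "is a continuous variable indicating the bi-weekly count from the start of the observation period". The decision coefficient is β4, on Int×Post. The SAP says that this "parameter from the regression model is interpreted in nearly the same manner as the primary outcome, in that it estimates the adjusted differential change", and it sets a decision rule: "We will consider the Code Sepsis intervention of have had an impact if" β4 is statistically significant and different from zero. On what the model permits, it says: "This model allows for the trends to differ between the intervention and control hospitals during the pre-intervention phase". It does not mention levels. Wash-in data are excluded, and "we will use generalized linear gamma regression to estimate the DID"; no link function is named.

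The primary model, under Data analysis, is "Y_{igt} = \beta_0 + \beta_1 Int_g + \beta_2 Post_t + \beta_3 (Int_g * Post_t) + \beta_4 Cov", which has a stand-alone Int term. The equation under Heterogeneity of treatment effect also has one. The list under Primary and secondary outcome analysis covariates contains only patient and presentation variables, with no hospital term.

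**The concern.** A segmented regression that compares two groups needs four things to differ freely between them or over time: level, slope, common step and differential step. This equation leaves out the difference in level. The two groups then share one adjusted intercept at Time = 0, and a constant difference between hospitals has to be represented by a differential slope and a differential step. β4 is therefore not the differential change unless the adjusted gap at study start happens to be zero.

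A zero gap is hard to take for granted. Protocol section 4.1 and Table 1 compare a tertiary teaching ED (89,000 visits a year) with two regional referral EDs staffed by other physician groups. Protocol section 3.1 reports five-fold variation between physicians in median door-to-antibiotic time, and longer delays when the ED is busy.

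The analysis exists to guard the causal claim against non-parallel pre-intervention trends, in a non-randomized study with one intervention hospital. Readers will take it as confirming or refuting the primary result. As written it could do either for the wrong reason.

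**Working it through.** The SAP gives no numerical result for this model, so there is no figure of its own to reproduce.

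**Inputs**

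- Pre-intervention 11/13/2018 to 11/12/2019 (365 days); wash-in 11/13/2019 to 2/12/2020 (92 days, dropped); post-intervention 2/13/2020 to 2/12/2021 (366 days). Source: SAP, Study phases and associated exposures.
- Time in two-week counts from study start. Source: SAP, Sensitivity analyses.
- 1,650 sepsis patients a year at the intervention ED and 2,200 at the control EDs; SD 75 minutes; target effect 16 minutes. Source: SAP, Power.
- α = 0.05 from the SAP, taken as two-sided.
- Baseline gap D (intervention minus control, after covariates): **assumed**, because the documents give only a pooled mean of 170 minutes.

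**Why the bias arises, by hand**

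Let the true difference between hospitals be a constant D, with no trend and no effect. The equation must fit this difference as s·Time + p·Post, without an intercept. With equal numbers before and after, least squares gives:

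- s = D · t̄(pre) / [mean of Time² (pre) + variance of Time (post)]
- p = D − s · t̄(post)

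Treat arrivals as uniform and let L be the length of the pre-period. Then t̄(pre) = L/2, mean of Time² (pre) = L²/3 and variance of Time (post) ≈ L²/12, so s = D(1/2)/(5/12)/L = 1.2 D/L. The middle of the post-period is at (365 + 92 + 183)/365 = 1.753 L. Hence p = D(1 − 1.2 × 1.753) = **−1.10 D**.

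**Exact design matrix (weighted least squares, two-week counts)**

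| Coding of Time | β4 ÷ D with no true effect |
|---|---|
| From 0, wash-in weeks counted | −1.09 |
| From 1, wash-in weeks counted | −1.11 |
| From 0, wash-in weeks skipped | −0.79 |
| From 1, wash-in weeks skipped | −0.81 |

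The ratio does not depend on how patients divide between hospitals.

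**Size in minutes (Time from 0, wash-in counted; SE of β4 = 7.1)**

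| D (min) | β4, no true effect | Declared significant | β4, true effect −16 |
|---|---|---|---|
| +10 | −10.9 | 33% | −26.9 |
| +15 | −16.4 | 63% | −32.4 |
| +20 | −21.9 | 86% | −37.9 |
| −15 | +16.4 | 63% | +0.4 |
| −20 | +21.9 | 86% | +5.9 |

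For D = 10, 10.9/7.1 = 1.53, and the chance of exceeding 1.96 in absolute value is about 33%; the other rows follow in the same way.

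**Gamma regression**

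With an identity link the ratio is −1.09 to −1.10. With a log link it is −1.09 on the log scale: D = +20 on a mean of 170 gives 170 × [exp(−1.093 × ln(190/170)) − 1] ≈ −19.5 minutes. In simulated gamma data (log link, 300 runs per setting, no true effect), β4 was significant in 16%, 32% and 83% of runs for D = 5, 10 and 20, and in 90% for D = −20.

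**With Int added**

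The bias is zero: for D = +20 and no effect, the Int coefficient is 20 and the step is 0. With a true effect of −16, the step is −16.0 at every D tried. Simulated rejection with no effect returns to 3% to 7%. The SE of the step becomes 8.2 minutes.

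**The case against.** The strongest reply is that this is a drafting slip. The SAP's two other model equations include Int, the analyses are to be run in R, and in an R formula the asterisk between Time and Int would bring in the Int main effect automatically. Nothing in the documents shows that a model without Int will actually be fitted. That is fair as to what the code may do. However, the SAP writes main effects out separately in its other equations, so the asterisk reads there as a plain product, and an analyst who follows this equation would omit the term.

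Second, the covariate vector is not redefined for this model, and the heterogeneity section describes it as including hospital-level variables. A hospital indicator there would cure the problem, but none is listed, and the primary analysis section calls the vector patient-level.

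Third, the gap is unknown and only its covariate-adjusted part matters. The multiplier also depends on coding. If Time skips the wash-in, the SE is 6.2 and the false-positive rates at 10, 15 and 20 minutes fall to about 24%, 48% and 72%. Centring Time in the middle of the pre-period or later would reverse the sign of the bias without removing it. These points qualify the size; the error remains.

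Fourth, the primary model includes Int and is unaffected, and the stated fallback if the parallel-trends test fails is propensity weighting, not this model. That limits the reach, but this analysis has its own rule for declaring an impact.

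**Conclusion.** The model is wrong as written. Unless the two sets of hospitals have the same adjusted door-to-antibiotic time at study start, β4 does not estimate the differential change that the SAP says it does. The bias is about −1.1 times the adjusted baseline gap with Time counted from study start through the wash-in, and about −0.8 times if the wash-in weeks are skipped; under a log link the ratio holds on the log scale. A 15-minute gap is enough to produce a spurious benefit as large as the effect the trial is powered for, or to cancel a real one. The multiplier follows from the SAP's own design. The gap is an assumption, and the significance rates also assume SD 75 and independent patients. The primary difference-in-differences estimate is not affected.

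**What to change.** Write the hospital main effect into the equation:

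Y = β0 + β1 Time + β2 Int + β3 (Time × Int) + β4 Post + β5 (Int × Post) + β6 Cov

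Base the decision on β5, the Int×Post coefficient, and keep the same terms under whichever gamma link is used. In the same edit, state the link, the origin of Time, and whether the wash-in weeks are counted. If the analysis code already includes Int, the text should be corrected to match it.

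The cost is one term in the SAP and the code, and a rise in the SE of the step from about 7.1 to 8.2 minutes (SD 75, independent patients). At that SE a 16-minute effect is 16/8.2 = 1.95 standard errors, so this analysis has only about 50% power for it. The SAP should therefore say that a non-significant step does not by itself contradict the primary result.

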## 3. TRIAL DESCRIPTION

#### 3.1 Background

Sepsis, the combination of infection and acute organ dysfunction, is a common, morbid, and often lethal syndrome. Sepsis hospitalizes 1.3 million patients each year, kills 20%, and costs \$23.7 billion. Early, appropriate antibiotic initiation is critical: sepsis survival decreases with every hour's delay.  While guidelines and government mandates thus emphasize prompt antibiotics, international guidelines' have admitted a lack of data to support the feasibility or implementation of their one-hour door-to-antibiotic goal.

Among patients presenting to the emergency department (ED) with sepsis, we previously found that non-patient contextual cues could improve rapid antibiotic initiation, whereas ED busyness was associated with delayed antibiotics. I also discovered five-fold variation between physicians in median door-to-antibiotic time. ED care reorganization could bypass these cognitive, stylistic, and resource barriers to timely sepsis treatment. In fact, ED protocols linking prehospital notification to a multidisciplinary, team-based response are common and effective for trauma, stroke, and myocardial infarction, conditions that are less common and less mortal than sepsis but require similarly time-sensitive treatment. Given that sepsis has a less definitive presentation, however, analogous protocols for sepsis could waste resources or promote anchoring bias and overtreatment of patients without sepsis, issues observed with door-to-antibiotic standards for pneumonia.

We hypothesize that reorganizing ED sepsis care around multidisciplinary "Code Sepsis" teams activated prior to or upon patients' ED arrival will reduce door-to-antibiotic times — with tolerable overtreatment rates — by mobilizing personnel, systematizing illness severity and infection risk assessment, facilitating test completion, and eliminating any gap between treatment decision and antibiotic infusion. This study will therefore evaluate the effectiveness and tradeoffs of a Code Sepsis program for ED sepsis patients.

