#### 4.2.5 Study phase dates

ED patients arriving to study EDs will be assigned to a study phase based on their ED arrival date.

- *Phase #1* (pre-intervention analysis phase): November 13, 2018 to November 12, 2019
- *Phase #2* (intervention roll-in): November 13, 2019 to February 12, 2020
- *Phase #3* (full intervention analysis phase): February 13, 2020 to February 12, 2021

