#### Study phases and associated exposures

Dhaca	Detient CD envivel deter	Care received by patients		
Phase	Patient ED arrival dates		Intervention EDs	
Pre-intervention analysis	11/13/2018-11/12/2019	Standard care	Standard care	
Post-intervention wash-in	11/13/2019-2/12/2020	Standard care	Code Sepsis protocol	
Post-intervention analysis	2/13/2020-2/12/2021	Standard care	Code Sepsis protocol	

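### The key interrupted time series has no seasonal term, so a seasonal difference between intervention and control EDs, which cancels in the primary difference-in-differences, can bias its beta4

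*SAP*

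**What the plan says.** SAP, Sensitivity analyses, gives the key model as "Y_{igt} = \beta_0 + \beta_1 Time + \beta_2 (Time * Int_g) + \beta_3 Post_t + \beta_4 (Int_g * Post_t) + \beta_5 Cov". Time "is a continuous variable indicating the bi-weekly count from the start of the observation period". The section adds that "Data from the wash-in phase will be excluded from the sensitivity analysis". The model's stated purpose is to strengthen causal inference from the primary result and to deal with non-parallel pre-intervention trends. It has its own decision rule: an impact is declared if beta4 is statistically significant.

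The analysis phases are "11/13/2018-11/12/2019" and "2/13/2020-2/12/2021" (SAP, Study phases and associated exposures; the same dates are in Protocol 4.2.5). Each is one full year.

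The covariates carried into this analysis (SAP, Primary and secondary outcome analysis covariates) are patient-level. Neither that list nor the propensity-score list under Data analysis contains month or season.

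**The concern.** A yearly cycle seen through a one-year window looks partly like a slope. The primary DID compares full-year means, so the cycle averages out even when it is specific to one hospital. The segmented regression instead fits a slope difference and carries it from one phase to the other, so whatever seasonal difference the slope picks up is passed into beta4.

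Such a difference is possible. The intervention ED is a tertiary teaching site with 89,000 visits a year, and the controls are regional referral sites with 49,000 and 65,000 (Protocol 4.1, Table 1). The hospitals serve different counties (Protocol 4.4). The protocol also reports that "ED busyness was associated with delayed antibiotics" (3.1 Background).

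At stake is how the robustness check is read. It could disagree with a sound primary result, or agree with an unsound one, for a reason unrelated to Code Sepsis. A disagreement could also be mistaken for a failure of parallel trends.

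**Working it through.** **Inputs.** Phase dates as above: 365 and 366 days, midpoints 457.5 days apart, or 457.5/365.25 = 1.25 years. Sepsis patients per year: 1,650 at the intervention ED and 2,200 at the controls; SD 75 minutes (SAP, Power). *Assumptions:* A is the amplitude of the intervention-minus-control seasonal difference, taken as a stable yearly sinusoid of 3 to 6 minutes; Time is calendar time, so the wash-in gap counts; identity scale; independent patients.

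**1. The plan's own figures.** None concerns seasonality. The nearest is 90% power for a 16-minute change. In closed form the DID standard error is 75 × sqrt(2/1650 + 2/2200) = 3.45 minutes. Two-sided 5% power at 16 minutes is then 99.6%, so the stated 90% is not reproduced. It errs on the cautious side, its simulation details are not given, and it does not bear on this point.

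**2. Primary DID.** Averaging a yearly cosine over each phase and differencing leaves at most 0.002A. It cancels.

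**3. Segmented regression with the Int main effect restored.** The bias in beta4 is the change in the mean difference (about 0) minus fitted slope × 1.25 years.
- The least-squares slope of a yearly cosine over a one-year window is −(12/2π) sin(2πp) A = −1.91 sin(2πp) A per year, where p is the fraction of a year from window start to peak.
- Phase 3 starts a quarter-year later in the cycle, so its slope is +1.91 cos(2πp) A.
- The single fitted slope is close to their average, so the bias is 1.25 × (1.91/2) × [sin(2πp) − cos(2πp)] A.
- Its maximum is 1.25 × 1.91/√2 = 1.69A. Least squares on the exact daily grid gives 1.67A, for a peak near 30 March (opposite sign near 28 September).
- For a 15 January peak, p = 63/365.25 = 0.172 and the bias is 1.25 × 0.955 × (0.884 − 0.468) = 0.50A.
- Averaged over all peak dates, the absolute bias is 1.07A.
- Adding a post-phase slope change as well, and reading the effect at the start of that phase, leaves a maximum of 1.71A.

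**4. The equation as printed (no Int).** The same fit, with patients weighted 4.5 to 6, gives a maximum of 0.94A, and 0.28A for a 15 January peak. Coding Time in two-week steps from zero makes the maximum 0.97A. If Time skips the wash-in gap, the maxima are 0.83A as printed and 1.34A with Int.

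**5. Are the different start months the cause?** Let both phases start on 13 November in consecutive years. The two slopes coincide and the midpoints are 1.00 year apart, so the maximum with Int is 1.91A (about 1.15A as printed). That is larger than with the actual dates. For a mid-January peak it is 1.69A with Int, against 0.50A.

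**6. Seasonality shared by all EDs.** The bias is 0 in both versions.

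**7. In minutes.**

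| | As printed | Int restored |
|---|---|---|
| Worst peak date, A = 3 to 6 | 0.94A = 2.8 to 5.6 | 1.67A = 5.0 to 10.0 |
| Mid-January peak, A = 3 to 6 | 0.28A = 0.8 to 1.7 | 0.50A = 1.5 to 3.0 |
| Standard error of beta4 | about 7.1 | about 8.3 |

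**8. Effect of harmonics.** With Int and group-specific annual harmonics, the bias from a yearly sinusoid is 0 and the standard error is about 9.6 minutes. Without Int, a constant level difference between hospitals already biases beta4 by about −1.10 minutes per minute. Adding harmonics to that equation makes it −1.39.

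**The case against.** The strongest reply is that this is a second-order matter in a sensitivity analysis. Four parts of it stand.

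- **A is hypothetical.** The documents say that busyness delays antibiotics and that the sites differ. They do not say that the sites have different yearly cycles. Infection source, temperature, acute physiology score, SOFA and arrival mode are all adjusted for and may absorb some seasonal case mix.
- **The remedy is a bias-variance choice.** Harmonics reduce mean squared error only if the bias removed exceeds sqrt(9.59² − 8.25²) = 4.9 minutes. At A = 3 the worst case is only about 5.0, and averaged over peak dates the break-even is near A = 4. Replacing the model outright is therefore not justified.
- **The missing Int main effect is the larger fault** in the same equation (step 8).
- **The scale is not settled.** The SAP specifies gamma regression without naming the link, and the multiples above are for the identity scale.

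A reader might also infer more than the documents support. One inference is that the November and February start dates create the bias; step 5 shows that matched starts would give a larger worst case. Another is that the 1.67 multiple applies to the printed equation; it applies only once Int is restored. A third is that a bias of some known number of minutes is present, which cannot be said without a value for A.

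The reply does not remove the structural point. The check is exposed to a nuisance that the primary analysis is not, and correcting the Int term alone increases that exposure.

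**Conclusion.** The point holds as a limited weakness of the key sensitivity analysis. With no seasonal term, an intervention-minus-control seasonal difference passes into beta4 through the projected slope, by an amount that depends on A and on the peak date. If A is in the assumed range, the worst case is of the same order as the standard error. A mid-winter peak would matter much less.

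The primary DID is not affected. The multiples rest on a stable yearly sinusoid, calendar time that includes the wash-in gap, and the identity scale. The conclusion supports an added version of the model, not a claim that the planned result will be wrong.

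**What to change.** In SAP, Sensitivity analyses, restore the Int main effect. Prespecify a version of the segmented regression with one annual pair (sine and cosine of day of year) and the products of both with Int. Report beta4 from this version alongside the version without harmonics, whatever the two show. Do not add the harmonics without the Int main effect, because that worsens the level-difference bias.

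The cost is SAP wording and four seasonal terms besides Int, with no new data. In the harmonic version the standard error of beta4 rises from about 8.3 to 9.6 minutes, roughly 16%. That version also assumes the same sinusoid in both years. Phase 3 falls in a period for which the SAP lists SARS-CoV-2 test result as a propensity covariate, so this assumption should be stated as a limitation.

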#### 5.2 Code Sepsis Protocol

The Code Sepsis protocol (Figure 3) has six steps developed in collaboration with ED-based study team members and ED leaders (including physicians, nurses, pharmacists, and others) from the implementation ED and the Intermountain system. The current draft protocol was further iteratively revised based on input derived from the proposed multidisciplinary team during *in situ* high-fidelity simulation and during informal/ad hoc operationally-oriented pilot testing of steps 1-5 during live patient care. The below protocol will be adapted further prior to and after implementation to ensure the protocol is feasible, efficient, and functions as intended based on stakeholder input and, as needed, additional protocol element testing during simulation and/or live patient care. Further revision will occur, during the protocol run-in phase and as needed based on observed findings and stakeholder input.

Figure 3. Current Code Sepsis protocol based on iterative revision using simulation testing, stakeholder input, & live pilot testing.

- Identify likely sepsis patient from prehospital notification call data (nurse), at ED triage (nurse/physician), or on ED room placement (nurse or physician), adapting local and national practice for stroke team activation.
- 2) Mobilize ED personnel and equipment to meet patients on arrival to the ED room using methods and communication networks already developed for ED trauma and stroke teams.
- 3) Concurrent patient evaluation and data collection by multiple disciplines (20-25 minutes), to include bedside assessment (e.g. history, examination, vital signs, allergy and medication history) by the physician, nurse and pharmacist; IV placement; blood and urine sampling; point-of-care laboratory testing, including lactate and urinalysis; and portable X-ray imaging. Appropriate therapeutic interventions will continue in parallel during the nominal data collection phase.
- 4) Team "huddles" to decide if sepsis diagnosis has been confirmed, disproven, or remains indeterminate. The physician may complete this step by announcing clinical decision-making to the team at any time. The nurse will request a decision huddle at 25 minutes into the Code Sepsis event if it has not previously been performed.

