- 5) Proceed with next therapeutic and/or diagnostic steps including, for confirmed sepsis patients, immediate initiation of an appropriate antibiotic regimen chosen from a range of options contained in a Code Sepsis antibiotic pack brought to the bedside by a pharmacist on protocol activation. Code Sepsis antibiotic regimens have been selected based on published guidelines and local antibiotic resistance patterns with input from ED clinicians, pharmacists, and infectious disease/antibiotic stewardship personnel.
- 6) If initial huddle pronounced sepsis status as "indeterminate," return to step #4 after additional 20-25 minutes to follow up on additional diagnostic results (e.g. urinalysis, complete blood count
- 7) For antibiotic-treated patients, follow-up by antibiotic stewardship pharmacist active de-escalation or cessation as appropriate.

Additional protocol elements/details:

- Code Sepsis team members:
  - ED attending physician +/- ED resident physician or medical student
  - ED triage nurse
  - ED unit coordinator (i.e. unit secretary)
  - o ED nurses x2
  - o ED patient care technician
  - ED phlebotomist x1-2
  - ED pharmacist as available
  - o ED X-ray technician
- Code Sepsis electronic order entry: Code Sepsis order sets for diagnostic evaluation and antibiotic treatment will be constructed and activated at the intervention ED's electronic medical record with the beginning of study Phase #2. Order sets will help speed up diagnostic testing and treatment initiation, aid care standardization, and facilitate Code Sepsis event tracking and data collection.
- Code Sepsis clinical team training: With active support from intervention hospital clinical leadership as well as Intermountain's system-wide ED leadership team, the Code Sepsis ED Implementation Team will provide clinical staff in the implementation ED with training on the Code Sepsis protocol during the months prior to study Phase #2. Primary training will include distribution of instructional materials, direct education at clinical staff meetings, targeted in-person education, and *in situ* simulation. Primary training will complete early in study Phase #2, with consolidation training, protocol reminders, physician detailing, and targeted clinician reeducation continuing through study Phase #3.

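### The key interrupted time series fits one intervention-versus-control slope to both phases, so its effect estimate equals the Phase 3 mean only if the effect is constant through Phase 3, a condition the SAP does not state

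*SAP*

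**What the plan says.** The SAP (Sensitivity analyses) names a multi-group interrupted time series as the key sensitivity analysis. Its stated purpose is "To augment causal inference from the primary analysis and evaluate for the possibility of non-parallel trends in the primary outcome". After an intercept and β1·Time, the equation continues "\beta_2 (Time * Int_g) + \beta_3 Post_t + \beta_4 (Int_g * Post_t) + \beta_5 Cov". Time "is a continuous variable indicating the bi-weekly count from the start of the observation period", so it does not restart at implementation. The slope term is explained with the sentence "This model allows for the trends to differ between the intervention and control hospitals during the pre-intervention phase". The intervention is declared to have had an impact if β4 is significant, and β4 is to be read almost as the primary estimate is read. On the roll-in the SAP says: "Data from the wash-in phase will be excluded from the sensitivity analysis".

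Section 5.2 of the protocol describes an intervention that can change after launch: "Further revision will occur, during the protocol run-in phase and as needed based on observed findings and stakeholder input". Primary training is to finish early in Phase 2, "with consolidation training, protocol reminders, physician detailing, and targeted clinician reeducation continuing through study Phase #3".

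**The concern.** Neither Time nor Time*Int is interacted with Post. The Time*Int coefficient is therefore one slope difference estimated from the pre and post phases together, not a baseline trend estimated from the baseline. If the effect drifts within Phase 3, part of that drift goes into Time*Int, is projected back over the baseline year and the roll-in gap, and comes off (or adds to) β4.

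The analysis exists to tell a real effect apart from a pre-existing differential trend. A learning curve in Phase 3 would look to this model like such a trend, so the check could appear to weaken a true primary result. A fading effect would be overstated and appear more robust than it is.

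**Working it through.** **Inputs.**
- Phases of 12 months pre, 3 months excluded, 12 months post (protocol 4.2.5).
- 1,650 intervention and 2,200 control sepsis patients a year; SD 75 minutes; target 16 minutes (SAP, Power).
- α = 0.05 (SAP, Data analysis), taken as two-sided.
- Assumed, not in the documents: the shape of the effect over Phase 3 (its mean is held at -16 minutes), equal baselines, no prior trend, independent patients.

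**The plan's own figure.** The plan gives no precision for the time series, only 90% power for 16 minutes in the difference-in-differences. With the annual counts in each phase:
- SE = 75·√(2/1650 + 2/2200) = 3.45, and power is 99.6%.
- Splitting each annual count over the two phases gives SE = 75·√(2/825 + 2/1100) = 4.89 and power 90.6%, close to the stated figure.

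The mismatch does not bear on this point. An SE of 3.45 is the benchmark for the primary analysis.

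**Algebra with Int included.** Take the intervention-minus-control difference: zero before, and in Phase 3 a mean m that strengthens by G minutes over the 12 months (G positive for build-up).
- The fitted common slope is the average of the two within-phase slopes: ½·(0 - G/12) = -G/24 per month.
- The phase midpoints are 15 months apart, so β4 = m - 15·(-G/24) = m + 0.625·G.
- At m = -16, the sign changes only if G exceeds 16/0.625 = 25.6 minutes.

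**As printed, without Int.** The two groups share an intercept, which limits what the slope can absorb. Noise-free weighted least squares on 26 + 26 two-week periods gives about one fifth of the Phase 3 slope absorbed (against one half with Int), and β4 ≈ m + 0.35·G.

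**Expected β4 (minutes), true Phase 3 mean -16:**

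| Effect across Phase 3 | As printed | With Int | With Int and post-phase slopes | Primary DID |
|---|---|---|---|---|
| Constant -16 | -16.0 | -16.0 | -16.0 | -16.0 |
| -12 to -20 | -13.2 | -11.0 | -16.0 | -16.0 |
| -8 to -24 | -10.4 | -6.0 | -16.0 | -16.0 |
| 0 to -32 | -4.8 | +4.0 | -16.0 | -16.0 |
| Build-up, plateau at 3 months | -12.0 | -8.9 | -16.0 | -16.0 |
| Build-up, plateau at 6 months | -8.5 | -2.7 | -16.0 | -16.0 |
| -24 to -8 (fading) | -21.6 | -26.0 | -16.0 | -16.0 |
| SE | 7.1 | 8.2 | 11.1 | 3.45 |
| Power for a constant 16 | 62% | 49% | 30% | 99.6% |

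Power is Φ(16/SE - 1.96). Time here is calendar time. The SAP does not say whether the two-week count runs through the excluded roll-in. If it skips it, the 0 to -32 ramp gives -6.4 as printed and 0.0 with Int.

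**Gamma check.** The SAP specifies gamma regression but no link. In 300 simulated trials per scenario (mean 170, SD 75, log and identity links) with the 0 to -32 ramp, the printed model averaged about -3.4 minutes and was significant in 7–8% of trials. The primary analysis was significant in 100%.

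**The case against.** The strongest reply is that a changing effect is assumed. Phase 2 is for launch and fine-tuning, Phase 3 is called full implementation, primary training ends early in Phase 2, and revision is only as needed. Continued reminders and re-education fit maintaining an effect as well as building one. This stands: the documents allow a changing effect and do not predict one, and with a constant effect the model is unbiased.

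A common slope is also a defensible trade of bias for precision. For the -8 to -24 ramp, root mean squared error is √(5.6² + 7.1²) ≈ 9.0 as printed, against 11.1 with post-phase slopes. This stands too, as a reason not to replace the simpler fit. It weakens once Int is included: √(10² + 8.2²) ≈ 12.9 against 11.1.

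The SAP's sentence about pre-phase trends is literally true, since the model does let them differ. It does not say that the same slope difference is imposed on Phase 3.

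A reader might infer that the SAP's model reverses the effect. The documents do not support that. With equal baselines the equation as printed shrinks the effect but keeps its sign in every scenario above. The +4.0 needs the steepest ramp, the Int term and a calendar time count. A reader might also infer that the primary result is at risk. It is not: impact is judged on β3, no passage lets β4 override it, and the SAP has a separate pre-test of parallel trends with propensity weighting if it fails.

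**Conclusion.** The point holds in conditional form. β4 equals the Phase 3 mean effect only if that effect is constant, and the SAP neither states this nor offers a fit that relaxes it. If the effect builds up, β4 as printed loses about 0.35 minutes for each minute gained across Phase 3 (0.625 with Int). If it fades, β4 is exaggerated by the same proportion. The sizes rest on the assumed shapes, equal baselines and no prior trend.

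The missing Int main effect is a separate defect: a 10-minute baseline gap moves β4 by about 11 minutes even for a constant effect (-27.0 or -5.0 instead of -16). Adding Int repairs that but increases the sensitivity to drift, so the two should be handled together. What is at stake is how the key sensitivity analysis is interpreted, not the primary estimate.

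**What to change.** In the SAP's Sensitivity analyses:

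1. Add the Int main effect to the equation, and state whether the two-week count runs through the excluded roll-in.
2. Keep the step-only fit, labelled as assuming a constant effect through Phase 3.
3. Add a second fit with Post*(Time - c) and Int*Post*(Time - c), where c is the midpoint of Phase 3. Time*Int then comes from the pre-phase only, and Int*Post is the effect at mid-Phase 3.
4. Report the primary difference-in-differences by quarter of Phase 3. Each quarter has SE = 75·√(1/1650 + 1/2200 + 1/412.5 + 1/550) ≈ 5.5 minutes, enough to show a marked drift.
5. State that a non-significant β4 in either fit is not evidence against the primary result.

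The cost is SAP wording and some extra analysis, with no new data and no change to the primary analysis. The downside is precision: the added fit has SE about 11.1 minutes against 8.2 for the step-only fit with Int, and about 30% power for 16 minutes. It also extrapolates a one-year baseline trend nine months beyond its end (the 3-month gap plus 6 months to mid-Phase 3). That is why it belongs beside the step-only fit and should not replace it.
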